
#### PROCEDURES:

Procedures will consist of running 4 cohorts of 14 high functioning adolescents with ASD (IQ≥70) and their parents in the STRW group or a social skills group (i.e., Program for the Evaluation and Enrichment of Relational Skills –PEERS ). Approximately 7 adolescents with ASD and their parents will participate in each STRW and PEERS group. Thus, across 4 cohorts, the goal will be to enroll 28 adolescents in both the STRW and PEERS groups during Years 1-4.

The parent will complete the Vineland-3 and the adolescent will be administered the SB-5 and the ADOS-2 if they do not have one that has been completed at CCHMC within the past 2 years. If the eligibility assessment indicates that inclusion criteria has been met, the adolescent and parent participants will complete the baseline assessment. At the baseline assessment, parents will complete an in-depth clinical interview to assess the DLS that will be targeted in the intervention and a questionnaire packet. Adolescent participants will complete activities to directly assess their DLS and a questionnaire packet. All procedures for the baseline visit except for the ADOS, IQ test, and Behavioral Observation may be conducted via telehealth. Adolescent and parent participants will also complete 3 DPDs (two weekdays and one weekend) after completing the baseline assessment visit. Once an eligible cohort of 14 adolescents with ASD has been obtained and completed measures at the baseline assessment visit, adolescents will be randomly assigned to either the STRW or PEERS intervention using a stratified randomized block design with IQ (≥85 and <85) and age (≥17 and <17) as strata variables to ensure balanced group assignment for each cohort. Thus, across 4 cohorts, the goal will be to enroll up to 28 adolescents in both the STRW and PEERS groups during Years 1-4.

Randomization: Once an eligible cohort of 14 adolescents with ASD has been enrolled and completed measures at the baseline assessment, adolescents will be randomly assigned to either STRW or PEERS using stratified random sampling. The stratification is based on IQ (IQ<85 and IQ≥85) and age (≥17 years and <17 years) and will be used to ensure balanced group assignment for each cohort. A simple randomization within the strata will be generated and subjects will be assigned to one of the two groups. The randomization will be conducted by an individual independent of the study in order to reduce any potential biases. The clinical research coordinator who will conduct the daily phone diaries with adolescents and parents, DLS GAS interview with parents, and direct behavioral observation measures with adolescents will be blinded to study arm.

The STRW Intervention consists of 14 weekly (90 minute) concurrent sessions that both adolescents with ASD and their parents attend. The main daily living skills (DLS) targeted including Morning Routine, Laundry, Kitchen/Cooking, and Money Management. These skills are taught to adolescents using evidence-based strategies such as video modeling, task analysis, technology, and direct instruction. Parents are taught to facilitate practice and generalization of these DLS to the home. Sessions are flexible and can be individualized to address the specific needs of adolescents with ASD and their parents. Due to COVID-19, an undetermined number of sessions will be conducted via telehealth using a HIPAA compliant version of Zoom.

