### Follow Up Outcomes Survey

Parents may complete a one-time 15-20 minute outcomes survey to assess their child's current status in education, work, independent living, social connectedness, and daily living skills after completing the intervention in the last 18-42 months. This will provide us with feedback for the interview we are developing to look at longer-term outcomes after completing the daily living skills intervention.

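### The protocol gives two different allocation methods for the same step, and the simple randomisation it describes cannot ensure the per-cohort balance it promises

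*Combined protocol and SAP*

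**What the plan says.** Both descriptions are in the Procedures section. They concern the same event: allocation of a full cohort of 14, after baseline measures, stratified by IQ (cut at 85) and age (cut at 17).

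- The general paragraph specifies allocation "using a stratified randomized block design with IQ (≥85 and <85) and age (≥17 and <17) as strata variables" and gives the purpose of the strata: "as strata variables to ensure balanced group assignment for each cohort".
- The Randomization paragraph says participants are "randomly assigned to either STRW or PEERS using stratified random sampling". It adds that the stratification "will be used to ensure balanced group assignment for each cohort" and then gives the mechanism: "A simple randomization within the strata will be generated and subjects will be assigned to one of the two groups".

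On group size, the same section says: "Approximately 7 adolescents with ASD and their parents will participate in each STRW and PEERS group". Study Design plans 28 per arm over four cohorts. No part of the document gives a block size, a rule for odd-sized strata, or a statement of which description governs.

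**The concern.** A blocked design restricts arm totals within each stratum; simple randomisation does not. They are different procedures, and whoever generates the list could follow either one and be in line with part of the protocol.

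The second description also defeats its own purpose. Independent fair assignments made stratum by stratum have the same joint distribution as independent fair assignments made with no strata. The IQ and age strata would then have no effect on the allocation.

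Two things are at stake. Both interventions are delivered to groups planned at about seven families, so a badly split cohort gives the two arms different group settings. And IQ and age were chosen so that the arms would match on them.

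**Working it through.** **Inputs from the protocol.** Four cohorts of 14; 1:1 allocation; four IQ-by-age strata, or 14/4 = 3.5 participants per stratum per cohort on average; Aim 1 gains of 11 and 4 months, SD 8.4, 24 completers per group (Power Analyses).

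**Assumptions not in the protocol.** Two-sided 5% test; stratum sizes; shares of participants above each cut-off.

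**1. The plan's own figure.** The effect size is (11 − 4)/8.4 = 0.833. A two-sample t test with 24:24 has power 80.7%, so the stated 80% with 24 per group reproduces. It assumes equal arms.

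**2. Arm sizes in one cohort under simple randomisation.** The number assigned to STRW is Binomial(14, 0.5), with 2^14 = 16,384 equally likely outcomes.

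| Split | Count | Probability |
|---|---|---|
| Exactly 7:7 | 3,432 | 0.209 |
| 8:6 or closer | 3,432 + 2 × 3,003 = 9,438 | 0.576 |
| 9:5 or worse | 16,384 − 9,438 = 6,946 | 0.424 |
| 10:4 or worse | 2 × (1,001 + 364 + 91 + 14 + 1) = 2,942 | 0.180 |

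**3. Four cohorts.**
- At least one is 9:5 or worse: 1 − 0.576^4 = 0.890.
- At least one is 10:4 or worse: 1 − (1 − 0.1796)^4 = 0.547.
- Over all 56, Binomial(56, 0.5) gives 32:24 or worse with probability 0.350.

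**4. Strata falling wholly in one arm.** A stratum of size s does so with probability 2 × 0.5^s. For at least one such stratum in a cohort, take 1 − Π(1 − 2 × 0.5^s) over strata with s ≥ 2.
- Sizes 4,4,3,3: 1 − (0.875² × 0.75²) = 0.569.
- Sizes 5,4,3,2: 0.692. Sizes 6,4,2,2: 0.788. Sizes 8,2,2,2: 0.876.
- Sizes 6,6,1,1: 1 − (1 − 2 × 0.5^6)² = 0.062, not counting the single-person strata.

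The nine possible splits with at least 2 per stratum span 57 to 88%. If stratum sizes are themselves drawn at random from the shares in step 5, the average is about 49 to 58%.

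**5. IQ and age balance over the whole trial.** This is a simulation of 15,000 trials of 4 × 14 per scenario, with IQ and age independent. The event is a difference between arms of 20 points or more in the share with IQ ≥85 or the share aged ≥17. The blocked rule is the one given under the fix.

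| Assumed share for each factor | Simple | Blocked |
|---|---|---|
| 50:50 | 25.7% | 0.09% |
| 60:40 | 24.6% | 0.05% |
| 70:30 | 19.7% | 0.08% |

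The blocked rule gave 7:7 in every simulated cohort. For one factor alone, the figure under simple randomisation is about 10 to 14%.

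**6. Power.** With 48 completers, power is 80.7% at 24:24, 79.6% at 20:28, and 79.8% averaged over Binomial(48, 0.5).

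**7. Ordinary blocking.** Blocks of 2 or 4 within each stratum, with odd leftovers settled separately, do not guarantee 7:7 either. With sizes 5,3,3,3, exact 7:7 occurs with probability 0.375 and 9:5 or worse with 0.125. The rule for leftovers therefore has to be stated.

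**The case against.** The strongest reply is that the Randomization paragraph can be read more kindly. It opens with stratified random sampling, and the whole cohort is known before allocation, so the mechanism sentence could mean drawing a random half of each stratum. That would agree with the blocked design and with the stated purpose. On that reading, with each odd stratum settled by its own coin toss and the shares assumed above, a cohort is 8:6 about 44% of the time and 9:5 or worse only about 1.5%. With exactly two odd strata, 8:6 has probability one half. A split of 8:6 fits a plan for approximately seven.

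This reading is possible, and the figures in steps 2 to 6 for simple randomisation do not apply under it. But the mechanism sentence does not say it, and odd strata would still have no rule.

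The harm is also limited, and these points stand:
- The imbalance is chance and does not bias the comparison. The average power loss is 80.7 − 79.8 = 0.9 points.
- The protocol sets no minimum or maximum group size. The telehealth STRW teen sessions appear to be run with one family at a time, where group size matters less.
- IQ is planned as a predictor (Measures) and the groups are to be compared before treatment (Analyses). Both help with covariate imbalance; neither restores group sizes.
- The 57 to 88% range in step 4 covers only splits with at least two per stratum; the random-size average is lower.

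Finally, the Follow Up Outcomes Survey contacts families "after completing the intervention in the last 18-42 months", so some cohorts may already be allocated. That changes what can be corrected. It does not remove the need to say which method was used.

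**Conclusion.** The concern holds and should be fixed. The two descriptions contradict each other, and the simple randomisation, in its ordinary sense, cannot ensure the cohort-level balance that both give as the aim.

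The arm-size probabilities are exact and need only independent 1:1 assignment. The stratum and covariate figures rest on assumed IQ and age distributions, because the protocol gives none; the power figures also assume a two-sided 5% test. The consequence is unequal therapy groups and avoidable IQ and age imbalance in a small trial. It is not a threat to validity or a material loss of power.

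**What to change.** For any cohort not yet randomised, replace the simple-randomisation sentence in the Randomization paragraph with one blocked method, and have the general Procedures paragraph refer to it. Suitable text:

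> Within each cohort, participants will be allocated 1:1 in permuted blocks of 2 within each of the four IQ-by-age strata; participants left over from strata with an odd count will be pooled and allocated in one balanced block.

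In a full cohort of 14 the number of odd strata is 0, 2 or 4, so the leftovers always divide evenly and the result is 7:7. Blocks of 2 are not predictable here because the whole cohort is assigned at once. If a cohort could go ahead with an odd number, add a rule for the one unpaired participant. Other restricted schemes would also serve, provided that a single scheme is stated in full.

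For cohorts already randomised, record the method actually used and report arm sizes by cohort and stratum.

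The cost is low: one sentence and a cross-reference, with no effect on recruitment, and a documentation note for past cohorts.

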### **STRW Intervention Group:**

### STRW In-Person Sessions:

### Adolescent Group Sessions.

Each week one DLS will be targeted. Through didactics, demonstration, role plays, small group activities, and direct teaching, therapists will discuss how to break down a target DLS into manageable steps and then work towards acquiring the DLS using effective evidence-based strategies for adolescents with ASD. Adolescents will work with therapists in small groups to learn and practice the skill in session. While not directly targeted, appropriate social skills will be modeled (e.g., listening to others, respecting others' opinions) and discussed when relevant (e.g., tips for interacting with cashiers when grocery shopping, effectively negotiating with parents using the behavior contract). The importance of acquiring DLS will be discussed in each session to increase understanding and foster motivation.

Parent Group Sessions. Each week parents will receive instruction and detailed information (e.g., handouts, online and print resources) and have an opportunity to practice strategies or approaches to promote skill acquisition, maintenance, and generalization of targeted DLS for adolescents with ASD. The content and activities of the adolescent sessions will be discussed in detail. Parents will be taught to use a behavior contract to increase adolescent motivation to engage in skill acquisition of targeted DLS in the home or community. The behavior contract, as it applies to each targeted DLS, will be reviewed each week and will be the primary method in which parents will motivate adolescents to work towards their DLS goals. Techniques to encourage independence will be discussed (e.g., fading prompts and rewards). The therapist in the parent group sessions will discuss the content of adolescent sessions in detail and also assist in problem solving any barriers (e.g., addressing decreased motivation from adolescent to work on DLS, developing parental skills to foster independence, cultural issues). Parents' skill acquisition and implementation will be further facilitated by the group process of sharing successes and problem-solving with each other.

### STRW Telehealth Sessions:

The STRW parent sessions will be facilitated via video, using the HIPAA compliant version of Zoom. The format will be similar to the in-person sessions.

The STRW teen sessions will be scheduled and run by a psychology post-doctoral fellow or graduate student trainee. The sessions will be scheduled for 1 hour, and both parent and teen will participate. Targeted daily living skills will be practiced using the participant's home appliances and materials.

### **PEERS Control Group:**

PEERS In-Person Sessions: PEERS is the control group and consists of 14 weekly (90 minute) concurrent sessions that both adolescents with ASD and their parents attend. Social-communication and interaction skills such as building friendships, handling arguments, dealing with teasing, arranging and attending outings with peers are targeted through direct instruction, modeling, and practice in adolescent sessions. Parents are taught how to build and reinforce social skills outside of sessions.

PEERS Telehealth Sessions: The PEERS parent and teen sessions will be run simultaneously using the HIPAA compliant version of Zoom. This will require families to have two devices so both parent and teen can attend sessions at the same time.

STRW and PEERS Follow-up visits: All randomized participants in the feasibility RCT will complete post-treatment and 6-month follow-up visits. Adolescent participants will complete a questionnaire packet and direct behavioral observation measures of their DLS. Parent participants will complete a questionnaire packet and clinical interview. All procedures for the post-treatment and 6 month follow up visits except for the Behavioral Observation may be conducted via telehealth. Both parent and adolescent participants will complete daily phone diaries (two weekdays and one weekend) after their post-treatment and 6-month follow-up assessment.

### Follow Up Outcomes Survey

Parents may complete a one-time 15-20 minute outcomes survey to assess their child's current status in education, work, independent living, social connectedness, and daily living skills after completing the intervention in the last 18-42 months. This will provide us with feedback for the interview we are developing to look at longer-term outcomes after completing the daily living skills intervention.

### **MEASURES:**

### Baseline only:

**The Background History Form** will collect demographics including race, ethnicity, maternal education, household income, and current treatments and services. Information obtained from the Background History form will be utilized to describe the sample and as covariates in statistical analyses.

The Autism Diagnostic Observation Schedule, 2nd Edition (ADOS-2) is a well-established clinician-administered diagnostic assessment. Either Module 3 or Module 4 of the ADOS-2 will be administered to all

adolescents at the baseline assessment to confirm ASD diagnosis. A previous ADOS may be used to confirm eligibility if was done less than 2 years ago or up to the discretion of the P.I. [name] is research reliable and a certified trainer of the ADOS-2. In addition to being suited to screen for eligibility, the ADOS-2 will be used to describe the sample and as a predictor in statistical analyses.

**The Stanford Binet Intelligence Scales, 5th Edition** (SB5) will be used to assess verbal, nonverbal, and overall cognitive abilities and will be administered at the baseline assessment. The SB5 will be used to confirm that the adolescent participant meets the inclusion criteria of a full-scale IQ >70 and will also be used as a predictor in statistical analyses.

## Baseline, Post-Treatment, and 6-Month Follow-Up:

The Vineland Adaptive Behavior Scales, 3rd Edition (Vineland-3) is a well-established standardized measure of adaptive behavior that assesses skills in the Communication, Daily Living Skills, and Socialization domains. The DLS domain is comprised of the Personal, Domestic, and Community subdomains and has items that directly correspond to goals being targeted in the STRW intervention. The Vineland-3 will be used at screening to confirm that the adolescent has deficient DLS (i.e., at least 1 of the 3 DLS subdomain standard scores is at least 15 points or more below full scale IQ). Raw scores and age equivalent scores on the DLS domain and subdomains will be used as a primary outcome measure.

## Daily Phone Diaries (DPDs)

The Daily Phone Diary uses a cued recall procedure to track adolescents with ASD and their parents through their activities over the past 24-hours and provides a fine-grained analysis of activity patterns, companions, level of prompting for activities, and mood 70,71. For all activities lasting five minutes or longer, a parent and their teen reports the type of activity, duration, and who was present. The interviewer assists the parent and teen in reconstructing his/her day as accurately as possible by providing prompts, such as the time of day or information about the previous activity ("after you finished dinner, what did you do next?"). Each activity is recorded by the interviewer on a computer with the time, a set of activities, companions, level of prompting/assistance, and a rating scale for mood ranging from 1 (Extremely Negative) to 5 (Extremely Positive). After completing each DPD, parents and teens will also be asked about their level of satisfaction with completing the DPDs. A set of 3 DPDs (2 weekdays and 1 weekend day) will be conducted by phone. The 24hour recall procedure was adapted for use with parents of children with asthma. The DPD has yielded reliable stability coefficients over a 3-week period (rs = .61-.71, p < .01) and high levels of interrater reliability (> 90%) in a cystic fibrosis population 70. Furthermore, strong convergent validity was found for parental differential treatment between the DPD and both home interview and nightly rating scale measures for parents of toddlers 71. Similarly, strong convergence (77-80% (Quittner et al., 1992)) was found for daily routines between the DPD and Self Observation Report Technique 72. Activity codes for the DPD are presented in Table 1. Both parents and adolescents will complete 1 set of 3-day diaries at each time point.

**Table 1. Activity Code Definitions** 

| Activity         | Definition  |
|------------------|---|
| Basic Child Care | Meeting the basic physical needs of the child (e.g., putting to bed, dressing) and facilitating child activities (e.g., driving to activities/school)   |
| Medical Care     | Caring for the child's health, including disease-specific treatment regimens (e.g. AED therapy, attending physician/clinic visits, and general health concerns (e.g., well visits, immunizations) |
| Household Tasks  | Engaging in general household chores, including cleaning, yard work, laundry, and grocery shopping  |

| Meals                       | Preparing and consuming food (e.g., making dinner, fixing snacks, eating lunch)   |
|-----------------------------|---|
| Recreation at home          | Engaging in leisure, relaxation, or social activities inside the home (e.g., reading, watching TV/movie, having friends over)                             |
| Recreation outside the home | Engaging in leisure, relaxation, or social activities outside of the home (e.g., going to mall, movie theater, visiting friends and family)               |
| Work/Attending School       | Engaging in paid employment in or outside of the home (e.g., driving to and from work, time at work)  |
| Self-care                   | Caring for one's own physical needs, including bathing, dressing, and personal hygiene  |
| Sleeping/Resting            | Engaging in naps or sleeping at bedtime   |
| Other                       | Includes all activities not encompassed in above categories, including time spent doing the DPD or one-time activities (e.g., wrapping gifts for a party) |

**Direct Behavioral Observations** will be developed and piloted through task analyses of targeted DLS (e.g., separating clothing and loading a washing machine, using cash to purchase an item at the store, making macaroni and cheese in the microwave, etc.) to obtain an objective measure of DLS in adolescents with ASD. The direct behavioral observations will be completed by the adolescent performing several specific DLS in the kitchen or life skills room at CCHMC. For example, the adolescent will be given all necessary materials (e.g., eggs, butter, milk, salt, pepper, bowl, whisk, pan, etc.) and told to "Make scrambled eggs on the stovetop." The assessor will utilize a task analysis that includes all of the steps for the target DLS to record the number of incorrect and correct steps performed by the adolescent. After the activity is completed, a percentage of steps performed independently will be calculated for each targeted DLS.]

The direct behavioral observations will be obtained at the baseline, post-treatment, and 6-month follow-up assessments.

The Daily Living Skills Goal Attainment Scale (DLS-GAS) will be created for each adolescent based on an in-depth clinical interview completed with the parent that assesses specific skills in all of the goals that will be targeted in the STRW intervention. The DLS targeted in STRW will be explicitly defined for each participant using GAS based on their current skill level. For example, for the targeted skill of laundry, parents will be asked to describe their adolescent's ability to independently separate clothes, use the washing machine and dryer, and fold and put clothes away. An independent clinical research coordinator who will not participate in any aspect of the STRW intervention will develop the DLS-GAS for each adolescent participant and evaluate change in goals on the DLS-GAS at post-treatment and 6-month follow-up assessments. The therapists facilitating the STRW intervention will not have access to the DLS-GAS. The DLS-GAS will be utilized as a primary outcome measure.

The *Adaptive Behavior Assessment System, 3rd Edition (ABAS-III)* is a parent and self-report measure that assesses adaptive behavior in the conceptual, practical, and social domains. The raw scores and T-scores will be utilized to compare parent and adolescent ratings of DLS.

The *Behavior Rating Inventory for Executive Function, 2nd Edition (BRIEF-2)* is a parent and self-report measure that assesses executive functioning across 8 scales including initiate, emotional control, shift, inhibit, organize/plan, organization of materials, and working memory. Raw scores for the scales and indices will be utilized to explore the relationship between executive function and participation in the intervention.

The **Social Responsiveness Scale, 2nd Edition (SRS-2)** is a 65-item parent-report measure that assesses social functioning in the areas of social awareness, social cognition, social communication, social motivation, and restricted interests and repetitive behavior. Raw scores and T-scores will be utilized to explore the relationship between social skills and participation in the intervention.

The *Behavior Assessment Scale for Children, 3rd Edition - Parenting Relationship Questionnaire* (*BASC-3 PRQ*), *Parent Rating Scales (BASC-3 PRS), Self-Report of Personality (BASC-3 SRP)*, the BASC-3 PRQ is a parent-report measure that assesses aspects of the parent-child relationship including attachment, communication, involvement, parenting confidence, and relational frustration. The PRS measures both adaptive and problem behaviors in the community and home setting. The SRP provides insight into a child's or adult's thoughts and feelings. Raw scores will be utilized to explore the relationship between parenting factors and participation in the intervention.

The *Helicopter Parenting Questionnaire* will be completed by adolescents and their parents and was adapted from another questionnaire. Five items, rated on a 5-point scale, assess parental involvement in making important decisions (e.g., solves any problem, intervenes in settling disputes with teachers). The raw score will explore the relationship between parental expectations and participation in the intervention.

The *Parental Expectations Questionnaire* will be completed by adolescents and their parents and was developed from the National Longitudinal Transition Study-2 to assess parental expectations in the areas of education, postsecondary school completion, and independence. Each item is scored on a 4-point Likert scale and the raw score will explore the relationship between expectations and participation in the intervention.

The **Family Quality of Life (FQOL) scale** will be completed by parents and has 5 domains that assess family interaction, parenting, emotional well-being, physical/material well-being, and disability related support. Each of the 25 items is scored on a 5-point Likert scale and the raw score on each domain will explore the relationship between family quality of life and participation in the intervention.

